# 4.3.1. Screening Phase (3-28 days)

It is estimated that approximately 1,220 subjects will be screened to allow approximately 795 subjects to be randomized at the Baseline visit. After obtaining informed consent, subjects will undergo all screening procedures as detailed in Table 1. All subjects who are screened into the study will be entered into the IWRS system. After all screening procedures are complete, subjects may return 3 to 28 days from signing informed consent to be randomized at the Baseline visit if they meet all eligibility criteria. Any subject who does not meet all eligibility criteria will be considered a Screen Failure.

Individuals who do not meet the criteria for participation in this study (screen failure) may be considered for re-screening in select circumstances (e.g., previously pregnant, screening window too long). Subjects who were considered screen failures may also be considered for re-screening provided the ineligibility was due to one of the eligibility criteria that may have changed due to medical intervention or one of the eligibility criteria modified in a protocol amendment. Adequate documentation in source records must support the previously failed criteria. In all possible re-screening circumstances, the situation may be discussed with the Sponsor prior to re-screening and a new subject number must be obtained from the appropriate study-related system. Re-screening will only be permitted one time.

# 4.3.2. Randomization Visit/Treatment Phase (Up to 45 days)

Subjects who meet all eligibility criteria will be randomized at the Baseline Visit via the IWRS. The subjects will be provided with an eDiary. The study personnel will instruct the subject on the proper use of the eDiary and ensure proper understanding and use of the tool, prior to the subject leaving the site.

After randomization via the IWRS, subjects will be dispensed the double-blind study drug to take home for up to 45 days. This study drug is to be taken when a migraine attack reaches moderate or severe intensity on the numeric rating scale (NRS) as indicated in the eDiary. Subjects will be instructed to take their study drug, as an outpatient, when (if) they have a migraine headache which reaches moderate or severe intensity **after they answer eDiary questions about their current pain and symptoms and identify their currently most bothersome, migraine associated, symptom (phonophobia, photophobia or nausea)**. The subject will complete an eDiary for 48 hours after taking study drug to record efficacy and other quality of life measures.

Subjects in this study may be randomized only once. Under no circumstances may a subject be re-randomized.

# 4.3.2.1. eDiary Data Collections

Subjects will record efficacy in their eDiary. A subject should not take study drug until the headache reaches moderate or severe intensity. Headache severity will be recorded using a 4-point numeric rating scale (no pain, mild pain, moderate pain, severe pain) at the onset of the migraine and after dosing at time points of 15, 30, 45, 60, and 90 minutes and 2, 3, 4, 6, 8, 24 and 48 hours. The presence or absence of associated symptoms (nausea, photophobia, phonophobia) and ratings of functional disability (4-point scale: normal, mildly impaired, severely impaired, requires bedrest) will be recorded at the same time points as the headache severity ratings. Subjects will also identify their currently most bothersome symptom before taking study drug. Subjects will record the date and time study therapy was taken in their
eDiary. Subjects who have headache pain reduced to a mild intensity or pain free intensity level will be considered to have achieved pain relief.

After taking study drug, all other headache medication is prohibited during the 2 hours post dose. However, a subject who does not experience relief of their migraine headache at the end of 2 hours after dosing with study drug (and after the 2-hour assessments have been completed on the eDiary) will be permitted to use the following rescue medication: aspirin, ibuprofen, acetaminophen up to 2000 mg/day, naproxen (or any other type of nonsteroidal anti-inflammatory drug (NSAID)), antiemetics (e.g., metoclopramide), or baclofen. These are the only medications allowed for rescue treatment after 2 hours post dose of study drug. However, if needed, after 48-hours of taking the single dose of study drug (and before returning for the End of Treatment Visit) subject may take their prescribed standard of care medications for treatment of migraine, including triptans if not contraindicated, provided all of the assessments have been completed on the eDiary. Exclusionary rescue medication such as, opioids, ergotamines, butalbital compounds, and muscle relaxants (except baclofen as a rescue medication, see above) are not allowed on this study. Similarly, if the migraine is relieved by study drug at 2 hours after dosing but then recurs to a moderate or severe intensity level between 2 and 48 hours, the subject will be permitted to take the same rescue medication as outlined above.

Subjects should be encouraged to treat the first qualifying (moderate to severe) migraine that occurs during the treatment phase. If subjects are unable to treat their first qualifying migraine due to scheduling, etc. the same medication restrictions would still apply (i.e. aspirin, ibuprofen, naproxen (or any other type of nonsteroidal anti-inflammatory drug (NSAID)), antiemetics (e.g., metoclopramide) or baclofen.

Similarly, for treatment of non-qualifying migraines (i.e. mild migraines, or other headaches) that occur during the treatment phase before a qualifying migraine is reported, subject will only be permitted to use the medications listed above. Triptans and acetaminophen (over 2000 mg/day) are prohibited after randomization except as rescue medication as described in Section 5.5. In all circumstances, the subject will continue to complete the eDiary for up to 48 hours after taking the study drug.

#### 4.3.3. Extension Phase

Not Applicable

# 4.3.4. End of Treatment

Subjects will return to the study site within 7 days of study drug dosing (+4 days) for review of the eDiary assessment of medication compliance and monitoring of tolerability and safety (including vital signs, laboratory tests, and electrocardiography). If a subject has NOT experienced a migraine headache of sufficient severity within 45 days after randomization, they still are required to complete all EOT visit procedures. All subjects must return unused study drug and eDiary to the study site.

# 4.4. Post Study Access to Therapy

At the end of the study the sponsor will not continue to supply study drug to subjects/investigators. The investigator should ensure that the subject receives the appropriate standard of care to treat the condition under study.

# **5. POPULATION**

Individuals entered in this trial will be subjects who suffer from migraines. The treatment setting for subjects may include headache clinics, hospitals or private practices, Subjects may be recruited from a variety of sources including referrals or professional recruitment agencies.

# 5.1. Number of Subjects

Approximately 1,220 subjects will be screened to randomize approximately 795 subjects (265 per arm). Subjects will be randomized in a 1:1:1 ratio to the rimegepant 25 mg, rimegepant 75 mg, or placebo treatment groups.

# 5.2. Inclusion Criteria

- 1. Signed Written Informed Consent
  - a. Written informed consent must be obtained from the subject in accordance with requirements of the study site's institutional review board (IRB) or ethics committee (EC), prior to the initiation of any protocol-required procedures.
- 2. Target Population; Subject has at least 1 year history of migraine (with or without aura) consistent with a diagnosis according to the International Classification of Headache Disorders, 3rd Edition including the following:
  - a. Migraine attacks present for more than 1 year with the age of onset of migraines prior to 50 years of age.
  - b. Migraine attacks, on average, lasting 4 72 hours if untreated.
  - c. Not more than 8 attacks of moderate to severe intensity per month within the last 3 months (month is defined as 4 weeks for the purpose of this protocol).
  - d. Subjects must be able to distinguish migraine attacks from tension/cluster headaches.
  - e. Consistent migraine headaches of at least 2 migraine attacks of moderate to severe intensity in each of the 3 months prior to Screening Visit and maintains this requirement during the Screening Period.
  - f. Less than 15 days with headache (migraine or non-migraine) per month in each of the 3 months prior to the Screening visit and maintains this requirement during the Screening Period.
  - g. Subjects on prophylactic migraine medication are permitted to remain on therapy if the dose has been stable for at least 3 months prior to the Screening Visit, and if the dose is not expected to change during the course of the study. Valproic acid/valproate is permitted if subject is on therapy for at least 6 months prior to the Screening Visit.
  - h. Subjects with contraindications for use of triptans may be included provided they meet all other study entry criteria.
- 3. Age and Reproductive Status

- a. Subjects  $\geq 18$  years
- b. Women of childbearing potential (WOCBP) with male partners and men with women partners of childbearing potential must be using 2 acceptable methods of contraception to avoid pregnancy throughout the study in such a manner that the risk of pregnancy is minimized. Males with vasectomy are considered surgically sterile provided the procedure occurred greater than 6 months (24 weeks) prior the Screening Visit.
- c. At the Baseline Visit, prior to dispensing Investigational Study Drug, WOCBP must have a negative urine pregnancy test (minimum sensitivity 25 IU/L or equivalent units of HCG).
- d. Women must not be pregnant, lactating or breastfeeding
- 4. Other Inclusion Criteria
  - a. No clinically significant abnormality identified on the medical or laboratory evaluation. A subject with a clinical abnormality or laboratory parameters outside the reference range may be included only if the investigator considers the finding not clinically significant, that it will not introduce additional risk factors, nor interfere with the study procedures.

#### 5.3. Exclusion Criteria

- 1. Target Disease Exclusion
  - a. Subject has a history of migraine with brainstem aura (basilar migraine), hemiplegic migraine or retinal migraine.
  - b. History of systemic use of analgesics (e.g. nonsteroidal anti-inflammatory drugs [NSAIDs] or acetaminophen) on ≥ 15 days per month during the 3 months (12 weeks) prior to the Screening Visit.
- 2. Medical History and Concurrent Diseases
  - a. (Deleted in a protocol amendment)
  - b. Subject history with current evidence of uncontrolled, unstable or recently diagnosed cardiovascular disease, such as ischemic heart disease, coronary artery vasospasm, and cerebral ischemia. Subjects with myocardial infarction (MI), acute coronary syndrome (ACS), percutaneous coronary intervention (PCI), cardiac surgery, stroke or transient ischemic attack (TIA) during 6 months (24 weeks) prior to screening.
  - c. Uncontrolled hypertension, or uncontrolled diabetes (however subjects can be included who have stable hypertension and/or diabetes for at least 3 months (12 weeks) prior to screening). Blood pressure greater than 150 mm Hg systolic or 100 mm Hg diastolic after 10 minutes of rest is exclusionary.
  - d. Subjects with major depressive episode within the last 12 months, major depressive disorder or any anxiety disorder requiring more than 1 medication for each disorder.

Medications to treat major depressive disorder or an anxiety disorder must have been at a stable dose for at least 3 months prior to the Screening visit.

- e. Active chronic pain syndromes (such as fibromyalgia, chronic pelvic pain, complex regional pain syndrome (CRPS)).
- f. Subjects with other pain syndromes (including trigeminal neuralgia), psychiatric conditions, dementia, or significant neurological disorders (other than migraine) that, in the Investigator's opinion, interfere with study assessments.
- g. Subject has current diagnosis of major depressive disorder requiring treatment with atypical antipsychotics, schizophrenia, bipolar disorder, or borderline personality disorder.
- h. Subject has a history of gastric, or small intestinal surgery (including Gastric Bypass, Gastric Banding, Gastric Sleeve, Gastric Balloon, etc.), or has a disease that causes malabsorption.
- i. Patient has any active hepatic or biliary disorder.
- j. The subject has a history or current evidence of any unstable medical conditions (e.g., history of congenital heart disease or arrhythmia, known or suspected infection, hepatitis B or C, or cancer) that, in the investigator's opinion, would expose them to undue risk of a significant AE or interfere with assessments of safety or efficacy during the course of the study.
- k. History of alcohol abuse and/or illicit drug use meeting DSM-V criteria for substance use disorder within 6 months of screening. Note, non-dependent use of cannabis/marijuana is permitted.
- 1. (Deleted in a protocol amendment)
- m. (Deleted in a protocol amendment)
- n. Body mass index >  $35 \text{ kg/m}^2$
- 3. Allergies and Adverse Drug Reactions
  - a. History of drug or other allergy which, in the opinion of the investigator, makes the subject unsuitable for participation in the study
- 4. Sex and Reproductive Status
  - a. Females of childbearing potential who are unwilling or unable to use an acceptable contraceptive method or abstinence to avoid pregnancy for the entire study period and for 60 days after the study.
  - b. Women with a positive pregnancy test on enrollment or prior to study drug administration.
- 5. Electrocardiogram (ECG) and Laboratory Test Findings

- a. Estimated glomerular filtration rate (eGFR)  $\leq$  30 ml/min/1.73m^2
- b. Corrected QT interval > 470 msec (QTc by method of Fridericia), at Screening
- c. Left Bundle Branch block (LBBB)
- d. (Deleted in a protocol amendment)
- e. (Deleted in a protocol amendment)
- f. Total bilirubin (T bili) > 1.5 × ULN (may be repeated once for confirmation during the screening period; direct bilirubin >1.5 × ULN is exclusionary for Gilbert's syndrome)
- g. AST or ALT >  $2.0 \times$  ULN (may be repeated once for confirmation during screening period)
- h. Neutrophil count  $\leq 1000/\mu L$  (or equivalent)
- i. HbA1c > 7.5%
- j. Other abnormal ECG that in the investigator's opinion makes the subject unsuitable for a clinical trial
- 6. Prohibited Medications
  - a. Subjects taking a prohibited medication (Refer to the Section 5.4)
- 7. Other Exclusion Criteria
  - a. Subjects who are compulsorily detained for treatment of either a psychiatric or physical (e.g., infection disease) illness
  - b. Exposure to non-biological investigational agents or investigation interventional treatments within the 30 days prior to Screening visit.
  - c. Exposure to biological investigational agents within the 90 days prior to Screening visit.
  - d. Subjects who have previously participated in any study of rimegepant.
  - e. Subjects who meet criteria for C-SSRS Suicidal Ideation Items 4 or 5 within the last 12 months prior to the Screening Visit, OR subjects who endorse any of the 5 C-SSRS Suicidal Behavior Items (actual attempt, interrupted attempt, aborted attempt, preparatory acts, or behavior) within the last 10 years prior to the Screening Visit, OR subjects who, in the opinion of the investigator, present a serious risk of suicide (See Section 6.2.5.)
  - f. Participation in any other investigational clinical trial while participating in this clinical trial.

- g. Subjects must complete the Baseline/ Randomization visit within 3 to 28 days of the Screening visit.
- h. Investigator site staff directly involved in the conduct of the study and their family members, site staff otherwise supervised by the investigator, and sponsor and sponsor delegate employees directly involved in the conduct of the study and their family members.

# 5.4. Prohibited and Restricted Concomitant Medications

The below medications are prohibited prior to randomization *and during the course of this study or as specified.* 

- 1. Traditional Chinese Medicines should not be taken 14 days prior to randomization and throughout the study.
- 2. St. John's Wort should not be taken 14 days prior to randomization and throughout the study.
- 3. Barbiturate-containing products (e.g. Fioricet, Fiorinal, butalbital, phenobarbital) should not be taken 14 days prior to randomization and throughout the study.
- 4. Modafinil (PROVIGIL®) should not be taken 14 days prior to randomization and throughout the study.
- 5. Butterbur root or extracts should not be taken 14 days prior to randomization and throughout the study.
- 6. History of use of ergotamine medications on greater than/equal 10 days per month on a regular basis for  $\geq$  3 months ( $\geq$  12 weeks).
- 7. Use of narcotic medication, such as opioids (e.g. morphine, codeine, oxycodone and hydrocodone) for at least 2 days prior to randomization.
- 8. History of systemic non-narcotic analgesic intake on ≥ 15 days per month for ≥ 3 month (e.g. acetaminophen, NSAIDs, gabapentin etc.) for other pain indications. (Please refer to Section 5.5 for rescue medication).
- 9. Use of acetaminophen or acetaminophen containing products must be discontinued at least 2 days prior to randomization (acetaminophen up to 2000 mg/day is allowed as rescue medication, see Section 5.5 ). During the screening phase (3-28 days) use of acetaminophen or acetaminophen containing products at daily dosing levels of greater than 2000 mg/day is prohibited.
- 10. The use of CGRP antagonist biologics [e.g. galcanezumab, erenumab, fremanezumab, eptinezumab-jjmr] is prohibited during the study. CGRP antagonist biologics must be discontinued 6 months prior to screening and are prohibited throughout the study.
- 11. The use of oral gepants must be discontinued 2 weeks prior to screening and are prohibited throughout the study (e.g. ubrogepant, atogepant). Any past exposure to rimegepant will be exclusionary.

- 12. Lasmiditan (Reyvow®) is prohibited 14 days prior to randomization and throughout the study.
- 13. Marijuana and all forms of ingested or inhaled cannabidiol and THC-containing products usage meeting DSM-V criteria for substance use disorder.
- 14. Muscle relaxants (baclofen is allowed as rescue medication, see Section 5.5).
- 15. Concomitant use of moderate to strong CYP3A4 inhibitors with rimegepant is prohibited during the study. If use of a moderate to strong CYP3A4 inhibitor is required, such as use of HIV Protease Inhibitors, Hepatitis C protease inhibitors, certain azole antifungals, or clarithromycin, dosing with rimegepant should be stopped and should not start again until 14 days after the last dose of a moderate to strong CYP3A4 inhibitor. Please see Section 16.1.
- 16. Concomitant use of moderate to strong CYP3A4 inducers with rimegepant is prohibited during the study. If use of a moderate to strong CYP3A4 inducer is required, dosing with rimegepant should be stopped and should not start again until 14 days after the last dose of a moderate to strong CYP3A4 inducer. Please see Section 16.1.
- 17. Concomitant use of strong inhibitors of the P-gp transporter with rimegepant is prohibited during the study. See Section 16.1.
- 18. Concomitant use of atypical antipsychotics such as Abilify® (aripiprazole), Zyprexa® (olanzapine), Seroquel® (quetiapine), Geodon® (ziprasidone), or Risperdal® (risperidone) is prohibited during the study.
- 19. Subjects on prophylactic migraine medication are permitted to remain on therapy provided they have been on a stable dose for at least 3 months prior to study entry.
- 20. Concomitant use of LAMICTAL® (lamotrigine) is prohibited during the study.
- 21. Use of CefalyTM or any other device for migraine treatment is prohibited within 12 weeks of the Screening Visit and during the study.
- 22. Low dose aspirin (e.g. up to 100 mg daily) for documented cardiovascular prophylaxis is allowed.

# 5.5. Rescue Medications

After dosing with study drug, all headache medication is prohibited during the 2 hours post dose. However, a subject who does not experience relief of their migraine headache at the end of 2 hours after dosing with study drug (*and after the 2-hour assessments have been completed on the eDiary*), will be permitted to use ONLY the following rescue medication: *aspirin, ibuprofen, acetaminophen up to 2000 mg/day, naproxen (or any other type of nonsteroidal anti-inflammatory drug (NSAID)), antiemetics (e.g., metoclopramide), or baclofen. These are the only medications allowed for rescue treatment after 2 hours post dose of study drug.* 

However, if needed, after 48-hours of taking the one dose of study drug (and before coming in for the End of Treatment Visit) subject may take their prescribed standard of care

medications for treatment of migraine including triptans if not contraindicated, provided all of the assessments have been completed on the eDiary. Similarly, if the migraine is relieved by study drug at 2 hours after dosing but then recurs to a moderate or severe intensity level between 2 and 48 hours, the subject will be permitted to take the same rescue medication as above. In all circumstances, the subject will always continue to complete the eDiary entries through the 48-hour assessment after taking the study drug. Use of concomitant medication after randomization, including rescue medication, will be recorded by the subject on a paper diary and reported to the site. The site will record medications that were taken within 14 days of taking study drug (or until the End of Treatment Visit).

During the 45 days the subject is participating in the study, if the subject has a nonqualifying migraine (mild migraine) or a migraine that they do not treat with study drug, the subject is permitted to use only the following medications: aspirin, ibuprofen, naproxen (or any other type of non- steroidal anti-inflammatory drug (NSAID)), antiemetics (e.g., metoclopramide), or baclofen.

After completing all assessments (through 48 hours and before End of Treatment Visit) in their eDiary, if subjects experience a migraine, they are allowed to take their standard of care medication (including triptans if not contraindicated and acetaminophen up to 2000 mg/day).

# 5.6. Women of Childbearing Potential

Women of childbearing potential (WOCBP) includes any female who has experienced menarche and who has not undergone successful surgical sterilization (hysterectomy, bilateral tubal ligation, or bilateral oophorectomy) or is not postmenopausal. Menopause is defined as:

- 1. Amenorrhea greater than or equal to 12 consecutive months without another cause and a documented serum follicle stimulating hormone (FSH) level > 35 mIU/mL at screening or
- 2. Woman with irregular menstrual periods and a documented serum follicle stimulating hormone (FSH) level > 35 mIU/mL at screening or
- 3. Women on hormone replacement therapy (HRT) who no longer menstruate

NOTE: FSH level testing is not required for women greater than or equal to 62 years old with amenorrhea of greater than or equal to one year

NOTE: Women on HRT who still menstruate and women with irregular menses should be considered as WOCBP

Women of childbearing potential and all male subjects must be counseled on and understand the requirements to avoid pregnancy, as well as acceptable methods of contraception to use throughout the study.

WOCBP with male partners and men with women partners of childbearing potential must use 2 acceptable methods of contraception to avoid pregnancy throughout the study and for up to 60 days (for WOCBP) and 90 days (for men) after the last dose of investigational product in such a manner that risk of pregnancy is minimized (i.e., this study begins with signed consent

form through 60 days (for WOCBP) and 90 days (for men) after dosing with study drug). It is required that all WOCBP use 2 methods of contraception for the duration of the study. The 2 methods should include one barrier method (i.e., condom with spermicidal gel, non-hormonal intrauterine devices, cervical cap etc.) and one other method. The other method could include hormonal contraceptives (e.g., oral contraceptives, injectable contraceptives, patch, or contraceptive implant [e.g., hormonal intrauterine device]) used since at least 4 weeks prior to sexual intercourse or another barrier method (note, an intrauterine device is considered one method).

Subjects who report abstinence, or who report exclusively being in same-sex relationships are still required to understand the contraception requirements in this study to prevent pregnancy. If subjects who report abstinence, or who report exclusively being in a same-sex relationship engage in heterosexual activity, then the contraception requirements must be followed.

Males with vasectomy are considered surgically sterile provided the procedure occurred greater than 6 months (24) weeks prior to the screening visit. Vasectomy is considered one form of contraception; therefore, one additional form of contraception must be used to fulfill the contraception requirements for the study. Male subjects must not donate sperm until 90 days following the last study drug administration.

All WOCBP must administer the home pregnancy test provided at home, prior to taking Investigational Study Drug. If the pregnancy test is positive, subjects should not take study drug and should immediately contact the Study Investigator.

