 Migraine History, history of triptan use and CV risk factors will be recorded on paper source documents and entered into the EDC. Subjects will also be asked about their typical most bothersome symptom when having a migraine.

 Height will only be captured at the Screening Visit. Weight, body temperature, respiratory rate, blood pressure and heart rate will be collected at all time points where indicated. Sitting arterial systolic and diastolic blood pressure and radial artery pulse rate will be measured.

 All screening visit laboratory test results must be received prior to Baseline (randomization) Visit. Refer to Section 6.2.4

- For WOCBP: A serum pregnancy test will be collected at the Screening and EOT Visit as part of the standard laboratory tests. Confirmatory urine pregnancy test for WOCBP will be completed on site at the Baseline Visit and any subsequent visits for confirmation at the Investigator's discretion. Home pregnancy test will be provided to WOCBP after completion of Baseline Visit. WOCBP subjects must complete the urine pregnancy test at home **prior** to taking study drug.
-  AE and SAEs must be reported from the time of informed consent. All ongoing non-serious AEs and SAEs will be followed to resolution or until investigator deems there will be no further status change. SAEs that occur during the treatment period should be reported to site according to local regulatory requirements. Non-serious AEs that occur during the treatment period should be reported to the site at the EOT.
-  The C-SSRS will be clinician administered on site with a paper form.
-  Subjects will be randomized in the IWRS system at the Baseline Visit (Randomization Day 01).
-  Subjects should be instructed that the dose should be taken once the migraine attack reaches moderate or severe pain and after the subject has completed all required migraine assessments in the eDiary. The eDiary will prompt the subject when they should take study drug.
-  Site staff to review and confirm entries with subjects and confirm all data points are transferred to the system and reset eDiary for future subject use, PRIOR to the subject leaving the clinic.
-  ± Windows for timeframe around efficacy assessments (15, 30, 45, 60, 90 min, 2, 3, 4, 6, 8, 24 and 48 hours) will be automated and captured in the eDiary.

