# 6.2.4.1. Laboratory Testing

Blood and urine samples will be obtained as outlined in Table 1 for clinical laboratory evaluations. A central laboratory vendor will be utilized for this study and a laboratory manual will be provided to each site. If possible, subjects should be fasting for a minimum of 8 hours prior to all blood draws. However, if a subject is not fasting at a given visit, the blood draw should still be performed, and the non-fasting status should be documented.

**Hematology**: Hemoglobin, hematocrit, red blood cell count, white blood cell count (WBC) with differential, and platelets.

**Chemistry**: Sodium, potassium, chloride, bicarbonate, calcium; glucose, BUN (urea), serum creatinine, uric acid, ALT, AST, alkaline phosphatase, LDH, total protein, albumin, T bili, direct bilirubin, indirect bilirubin, CK, HbA1c.

End of Treatment Visit:

- Elevations in CK (>5 × ULN) may have further CK fractionation tests performed through the central lab.
- Elevations in AST/ALT [≥3 × ULN in subjects with AST/ALT baseline value within normal range; AST or ALT ≥2 times the baseline values AND ≥3 × ULN, or ≥8× ULN (whichever is smaller) in subjects with AST or ALT baseline values above the normal range] or T bili [≥2 × ULN in subjects with T bili baseline value within normal range with no evidence of hemolysis and an alkaline phosphatase value <2 × ULN or not available; T bili level increased from baseline value by an amount of ≥1 × ULN or if the value reaches ≥3 × ULN (whichever is smaller) in subjects with T bili baseline values above the normal range] may have reflex to GGT, HAV antibody (HAVIgM), Hepatitis B Surface Antigen (HBsAg), Hepatitis B Core Antibody (HBcIgM) and Hepatitis C Antibody (HCVAb)

Lipid panel: Cholesterol, LDL, HDL, triglycerides.

**Estimated glomerular filtration rate**: eGFR will be calculated and reported by the central lab at each visit that clinical laboratory tests are collected as outlined in Table 1.

**Urinalysis:** pH, specific gravity, ketones, nitrites, urobilinogen, leukocyte esterase, protein, glucose and blood. If blood, protein or leukocytes are positive and determined clinically significant by the investigator, then the subject should be asked to return for an unscheduled visit for microscopic examination.

Urine Drug Screen: For drugs of abuse.

FSH: For WOCBP at screening, to determine WOCBP status, if required.

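### Protocol 5.6 classes women with irregular menses and screening FSH above 35 mIU/mL as both postmenopausal and of childbearing potential, leaving three of four pregnancy tests and the contraception duty unsettled

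*Protocol*

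**What the plan says.** Section 5.6 defines WOCBP as women past menarche who are neither surgically sterilized nor postmenopausal, and then gives three routes to menopause. The second is "Woman with irregular menstrual periods and a documented serum follicle stimulating hormone (FSH) level > 35 mIU/mL at screening". The second NOTE below the list says "Women on HRT who still menstruate and women with irregular menses should be considered as WOCBP".

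Several duties are tied to WOCBP status:

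- **Serum tests**, Table 1 pregnancy-test footnote: "For WOCBP: A serum pregnancy test will be collected at the Screening and EOT Visit as part of the standard laboratory tests".
- **Baseline urine test**, Section 5.2, inclusion 3c: "At the Baseline Visit, prior to dispensing Investigational Study Drug, WOCBP must have a negative urine pregnancy test".
- **Home urine test**, Section 5.6: "All WOCBP must administer the home pregnancy test provided at home, prior to taking Investigational Study Drug".
- **Contraception**, Section 5.6 and inclusion 3b: two methods during the study and through 60 days after dosing.
- **Exclusion 4a**, Section 5.3, which removes "Females of childbearing potential who are unwilling or unable to use an acceptable contraceptive method or abstinence to avoid pregnancy".

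On FSH itself, Section 6.2.4.1 says it is measured "For WOCBP at screening, to determine WOCBP status, if required". Table 1 requires all screening laboratory results to be in before the Baseline Visit.

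**The concern.** The same woman is postmenopausal under one line of Section 5.6 and a WOCBP under another. A site could reasonably follow either, so handling may differ between sites or between subjects at one site.

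What is at stake is fetal exposure. Section 1.4 says there are no adequate data on developmental risk, and relies on pregnancy testing and two-method contraception to manage that risk. For this group those safeguards are not clearly switched on or off, although by the wording of the menopause definition itself these women still have periods. Entry is open from age 18 with no upper limit, so perimenopausal women can enrol.

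**Working it through.** **1. Who is affected.** Take women who are not surgically sterilized and have irregular menses:

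| Screening FSH | Menopause definition 2 | NOTE | Conflict? |
|---|---|---|---|
| 35 mIU/mL or below | not met, so WOCBP | WOCBP | no |
| not measured | not met, so WOCBP | WOCBP | no |
| above 35 mIU/mL | met, so not WOCBP | WOCBP | **yes** |

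Only the last row is in dispute.

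**2. Whether another section settles it.** Section 6.2.4.1 says FSH is drawn to establish WOCBP status. That gives the second menopause definition a use, but the first definition (amenorrhea of at least 12 months) also needs an FSH result. The laboratory text therefore does not show that the second definition overrides the NOTE. Section 6.2.4.2 on pregnancy testing does not rank the two lines either.

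**3. Which tests depend on the answer.** Table 1 schedules four pregnancy tests. The screening serum sample is taken at the visit where FSH is drawn, before the FSH result can reclassify the woman, so in practice it is done under either line. The other three come after the result is known.

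| Test | Under the NOTE | Under definition 2 |
|---|---|---|
| Screening serum | done | done (status not yet known) |
| Baseline urine | required | not required |
| Pre-dose home urine | required | not required |
| End of Treatment serum | required | not required |

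Tests that depend on the line followed: 4 − 1 = 3. Two of these three fall before dosing. The contraception duty and exclusion 4a switch in the same way.

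**4. Age of the one remaining result at dosing.** Section 4.3.1 says "subjects may return 3 to 28 days from signing informed consent to be randomized at the Baseline visit", and Section 4.3.2 allows up to 45 days between randomization and dosing.

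- Shortest: 3 + 0 = 3 days.
- Longest: 28 + 45 = 73 days.

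This assumes that blood is drawn on the day the 3-to-28-day count starts.

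**5. What still applies under definition 2.** Inclusion 3d and exclusion 4b bar pregnant women whatever their WOCBP status. For this group, though, no scheduled test after screening would reveal a pregnancy.

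**The case against.** The strongest reply is that the NOTE mirrors the list above it. Its first half, on HRT users who still menstruate, is the counterpart of the third menopause definition. Its second half can be read as the counterpart of the second definition, meaning irregular menses without the documented FSH. On that reading the specific laboratory criterion wins, and if the NOTE always governed, the second definition would never apply to anyone. This may well be what the sponsor meant. But the NOTE states no FSH limit, so a site would have to supply the condition itself.

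Other points stand in part:

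- The End of Treatment serum test comes after dosing and cannot prevent exposure. Section 6.2.4.2 also words the serum tests as done if appropriate, without limiting that sentence to WOCBP, so the loss of that test is less certain than the loss of the two urine tests.
- Seventy-three days is a ceiling. Subjects must have at least two moderate-to-severe attacks per four-week month and are encouraged to treat the first qualifying one, so most intervals should be well below it.
- The contraception duty bears on women with male partners, and abstinence is accepted.
- Whether irregular menses with FSH above 35 mIU/mL is an adequate clinical criterion is for the sponsor's clinicians, and nothing in the documents decides it.

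None of these removes the contradiction. They limit its size and leave the choice of remedy partly to clinical judgment.

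**Conclusion.** The concern holds. Section 5.6 gives two opposite classifications for one defined group and no rule of precedence. For each affected woman, three of four scheduled pregnancy tests and the two-method contraception duty depend on the line a site follows. Under the menopause definition, the only scheduled pre-dose result is 3 to 73 days old at dosing.

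The count of three is inferred from the order of the screening sample and the FSH result. Read literally, the Table 1 footnote limits all four tests to WOCBP, so three is the practical and more cautious figure. The number of women affected is not given and may be small, and each receives one dose. The efficacy analysis, alpha and sample size are not affected. This is a subject-safety inconsistency that should be corrected.

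**What to change.** Preferred: delete the second menopause definition in Section 5.6. Women with irregular menses are then WOCBP whatever their FSH, in line with the NOTE, and FSH still serves the first definition. This is the conservative choice. It costs one deleted line in the next amendment and, for each affected woman, three further pregnancy tests and the contraception requirement, with possible exclusion under 4a if she cannot meet it.

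If the clinical team wants to keep the second definition, amend the NOTE so that irregular menses makes a woman WOCBP only when no screening FSH above 35 mIU/mL is documented. In that case also limit the second definition to women not on HRT. Otherwise an HRT user with irregular periods and a high FSH would still meet both that definition and the first half of the NOTE. This route costs a reworded line or two and adds no tests, but it accepts that these women are dosed with no scheduled pregnancy test after screening.
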